Appendix A – Data Collection Sheet

OR Date: _____ Surgeon: _____

Case ID (e.g. 071619A): _____ Hospital: _____

Stapler Type (Circle): AEON™ Endostapler Echelon Flex™ Powered Stapler System

Patient Medications: _____

Patient Gender: _____ Patient Age: _____ Patient BMI: _____

AEON™ Endostapler	Black 60mm	Purple 60mm	Purple 45mm	Orange 60mm	Orange 45mm	Tan 60mm	Tan 45mm
Quantity Reloads Used							

Echelon FLEX™	Black 60mm	Black 45mm	Green 60mm	Green 45mm	Gold 60mm	Gold 45mm	Blue 60mm	Blue 45mm	White 60mm	White 45mm
Quantity Reloads Used										

Intraoperative Outcomes			
Product malfunction (circle)	Yes	No	N/A
Blood transfusion due to staple line bleeding (circle)	Yes	No	N/A

Surgeon overall satisfaction with the stapler used (circle): Dissatisfied Somewhat dissatisfied Neutral Somewhat satisfied Satisfied

Postoperative Outcomes			
Blood transfusion due to staple line bleeding within 72 hours of surgery start time (circle)	Yes	No	N/A
1 Week			
Dysphagia present (circle)	Yes	No	N/A
Nausea present (circle)	Yes	No	N/A
Weight loss:			
Pain level per standard protocol:			
1 Month			
Postoperative leakage during one-month monitoring period following procedure (circle)	Yes	No	N/A
Reported device-related adverse events (circle)	Yes	No	N/A
If yes, please specify:			

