The following two tables contain the available AEON™ Endostapler Reloads, as well as the similar products that they may replace. This is meant as a guide, and the surgeon should read and follow the Instructions for Use and use their own clinical judgment to determine appropriate products to use.

Table 1. Available AEON™ Endostapler Reloads

Reload Type	Cartridge Length	Product Code	Open Staple Height	Closed Staple Height	Minimum Port Size
Gray	45mm	AESR45G	2.0mm	0.75mm	12mm
White	45mm	AESR45W	2.5mm	1.0mm	12mm
White	60mm	AESR60W	2.5mm	1.0mm	12mm
Orange	45mm	AESR45R	3.25mm	1.5mm	12mm
Orange	60mm	AESR60R	3.25mm	1.5mm	12mm
Purple	45mm	AESR45P	4.0mm	1.8mm	12mm
Purple	60mm	AESR60P	4.0mm	1.8mm	12mm
Black	60mm	AESR60B	5.0mm	2.2mm	15mm

Table 2. Approximate Equivalence for AEON™ Endostapler Reloads

AEON™ Endostapler			Echelon Flex™		
Cartridge Color	Open Staple Height (mm)	Closed Staple Height (mm)	Cartridge Color	Open Staple Height (mm)	Closed Staple Height (mm)
Gray	2.0	0.75	Gray	2.0	0.75
White	2.5	1.0	White	2.5	1.0
Orange	3.25	1.5	Blue	3.5	1.5
Purple	4.0	1.8	Gold	3.8	1.8
Purple	4.0	1.8	Green	4.1	2.0
Black	5.0	2.2	Black	4.2	2.3

STUDY DETAILS

Patients will be screened based on the inclusion and exclusion criteria below and will be consecutively evaluated for study enrollment. Each case will be randomly assigned to one of the two FDA approved endoscopic staplers. For the purposes of this study, the surgeons will either use the AEON™ Endostapler or the Echelon Flex™ Powered Stapler system from Ethicon. Enrollment will be contingent on meeting these criteria, and the use of either the AEON™ Endostapler or the Echelon Flex™ Powered Stapler system from Ethicon. Study participation will begin once the subject signs the consent form and will end after the one-month postoperative follow up visit.

Selection of Subjects:

Inclusion Criteria

- Patients undergoing planned laparoscopic sleeve gastrectomy with signed surgery consent form
- Informed consent for study obtained and signed from each subject

Exclusion Criteria

- Planned open surgical approach
- Prior bariatric operation (i.e. revisional bariatric surgery)
- Use of staple line reinforcement material (buttress)
- Patients taking anticoagulants
- Patients under the age of 18 on the date of the surgery

Withdrawal of Subjects:

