Subjects are free to withdraw from the study at any time for any reason. Every effort will be made to determine why any subject withdraws from the study prematurely and this information will be recorded in the Clinical Study Report.

In addition, subjects may be withdrawn from the study by the Principal Investigator in consultation with the Sponsor for the following reasons:

- Adverse event
- Protocol violation
- Loss to follow-up

If a subject withdraws prematurely, all data normally collected by study completion should be collected at the time of premature discontinuation or at the scheduled discharge. All subjects who withdraw from the study with an ongoing adverse event must be followed until the event is resolved or deemed stable. At the discretion of the PI, additional follow up visits may be done for subject safety.

Withdrawn subjects will be replaced, until 60 subjects complete the study.

Primary Outcome Measure:

- Incidence of intraoperative staple line bleeding as measured by the provided bleeding severity scale

Secondary Outcome Measures:

- Incidence of postoperative leakage during one-month monitoring period following procedure
- Incidence of reported device-related adverse events
- Incidence of product malfunction during procedure
- Incidence of intraoperative or postoperative blood transfusion within 72 hours of surgery start time
- Postoperative pain level per standard protocol

Steps and Procedures:

The study will include 60 total consecutive cases, randomized for stapler type: 30 with the AEON™ Endostapler and 30 with Echelon Flex™. Surgeries will be performed by either [name], [name], or [name], with at least 5 surgeries of each stapler brand per surgeon.

All patients will undergo the standard preoperative evaluation pathway. Patients must sign informed consent for the operation.

All firings with the AEON™ Endostapler will be done with EASY/THICK MODE for the purposes of this study and shall conform to the AEON™ Instructions For Use (Appendix C). All firings with the Echelon Flex™ should be done according to the Echelon Flex™ Instructions for Use.

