In order to measure the primary outcome of incidence and degree of staple line bleeding, a third-party blinded primary outcome evaluator will be used. No sutures, cautery or clips shall be applied to the staple line during stapling, unless required at surgeon's discretion. Following the last firing, a member of the surgical or nursing team or the research coordinator present for the case will count 10 seconds and then capture an image with the laparoscope. The visual should be clear and portray the entire length of the staple line. In the event that bleeding from the staple line requires control prior to the last firing, an additional image should be captured before applying sutures, cautery, clips, etc. These photographs will then be sent by the research coordinator to the primary outcome evaluator either electronically or by mail. The primary outcome evaluator will be blinded to both the surgeon and device of each case. Upon receipt of photographs, the evaluator will evaluate staple line bleeding according to a provided bleeding severity scale and record results in the Bleeding Severity Evaluation Sheet (Appendix B). If a case has more than one image associated with it, the primary outcome evaluator will consider all images when selecting a bleeding severity level.

At the end of each case, the surgical team will fill out the relevant sections of the Data Collection Sheet (Appendix A). Case ID is captured as day/month/year, followed by surgery count for the day – e.g. 071619A for the first surgery performed on July 16, 2019.

All typical post-operative care will continue, including immediate post-operative care prior to hospital discharge as well as the standard one-week and one-month post-operative evaluation. At the end of both the one-week and one-month post-operative period, a member of the surgical or nursing team will fill out the relevant sections of the Data Collection Sheet.

There will be no follow up study data collected after this point, however the patients will continue the standard follow up regimen per the physician's practice.

Surgery Locations:

Surgeries will take place at Southern Surgical Hospital ([name]), Crescent City Surgical Centre ([name]), or Avala Hospital ([name]).

Termination of the Study:

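### The enrolment rule depends on which stapler was used, and the case form does not separate the assigned stapler from the one used, so a randomised case could be dropped or counted in the wrong arm

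*Combined protocol and SAP*

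**What the plan says.** **Allocation and enrolment.** Study Details states: "Each case will be randomly assigned to one of the two FDA approved endoscopic staplers". Steps and Procedures gives the split as "randomized for stapler type: 30 with the AEON™ Endostapler and 30 with Echelon Flex™". Study Details then adds a condition: "Enrollment will be contingent on meeting these criteria, and the use of either the AEON™ Endostapler or the Echelon Flex™ Powered Stapler system". The same paragraph starts a subject's participation at the signing of consent.

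**Recording.** The surgical team completes its part of Appendix A when the case is over (Steps and Procedures). The device item there is "Stapler Type (Circle): AEON™ Endostapler Echelon Flex™ Powered Stapler System": two options, one circle, no item for the stapler assigned, and none for a switch or its reason. Below it are reload-count rows, one set per brand. Malfunction is a yes, no or not-applicable item that does not name a device, although "Incidence of product malfunction during procedure" is a secondary outcome. Appendix B, which carries the blinded bleeding score, identifies the case only by Case ID. That ID is built from the date and the order of surgery on the day, not from a randomisation number.

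**Analysis.** The Statistics section leaves the methods to the Clinical Study Report. Protocol Deviations allows subjects with major deviations to be excluded case by case. Withdrawal of Subjects lists protocol violation as a reason for withdrawal and replaces withdrawn subjects until 60 complete. No section says that cases are analysed in the arm to which they were randomised.

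**The concern.** There are two separate weaknesses.

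1. Use of a stapler happens after assignment. If it is a condition of enrolment, membership of the study is partly settled by an event that the assigned device could influence. A case that was randomised and then completed with neither study stapler fails the condition as written.

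2. The blinded score on Appendix B reaches an arm through the Case ID and the circle on Appendix A. When both brands are fired in one case, that circle has no defined meaning. One team may circle the stapler assigned, another the one that finished the case. The malfunction item has the same gap: a yes beside the circled brand does not establish that the circled brand failed.

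The randomised comparison of bleeding is at stake, and so is the attribution of malfunctions between two manufacturers' devices. With 30 per arm, one or two cases are enough to move the estimate. Surgeons are not masked, so the reason for a switch is best written down when it happens rather than reconstructed later.

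**Working it through.** The plan has no figure to reproduce. The Statistics section says no sample size calculation was made, and the documents give no bleeding rate, malfunction rate or switching frequency. The check is therefore a reading of the sections together, followed by an illustration on assumed counts.

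**Step 1. What each rule does to each kind of case**

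| Case | Enrolment condition | Appendix A circle | Analysis rule |
|---|---|---|---|
| Assigned stapler throughout | met | unambiguous | none needed |
| Both study brands fired | met, since either suffices | assigned or used: undefined | none stated |
| Neither study brand used | not met | no option fits | none stated |

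The enrolment wording therefore affects only the third row. The risk of misplacing a case in the second row comes from the single circle together with the missing analysis rule.

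**Step 2. What the reload rows add.** If both brands' rows are filled in, the case is visibly mixed. The counts carry no order of firing, no assignment and no link to a malfunction.

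**Step 3. Size of a misplacement.** Inputs: 30 per arm (Steps and Procedures). Assumed: the same number *x* of bleeding cases in each arm, and *k* bleeding cases assigned to A but circled as B. By assigned stapler the difference is x/30 − x/30 = 0. By circled stapler it is

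(x + k)/(30 + k) − (x − k)/(30 − k).

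With *x* = 10:
- *k* = 1: 11/31 − 9/29 = 35.5% − 31.0% = 4.4 points (from unrounded values)
- *k* = 2: 12/32 − 8/28 = 37.5% − 28.6% = 8.9 points

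Over other assumed rates:

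| *x* per arm | *k* = 1 | *k* = 2 | *k* = 3 |
|---|---|---|---|
| 6/30 | 5.3 | 10.7 | 16.2 |
| 9/30 | 4.7 | 9.4 | 14.1 |
| 15/30 | 3.3 | 6.7 | 10.1 |

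**Step 4. Size of a dropped case.** If one bleeding case in A is dropped because neither study stapler was used, and is not replaced, the arms at *x* = 10 read 9/29 v 10/30: 33.3% − 31.0% = 2.3 points.

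**Step 5. Effect on a test (two-sided Fisher exact, assumed counts).** With no true difference, 8/28 v 12/32 gives p = 0.59, so two misplaced cases do not create a significant result. With 9/30 v 15/30 by assignment, p = 0.187. Moving two bleeding cases out of the 9/30 arm gives 7/28 v 17/32, p = 0.036. Moving two out of the 15/30 arm instead gives 13/28 v 11/32, p = 0.431. The direction depends on which arm loses the cases.

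**The case against.** **The sheet can already show mixed use.** This stands in part. The reload rows make a silent misclassification less likely. They do not identify the assigned arm or the device that failed.

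**The assignment may be held elsewhere.** A reader might infer that the randomised arm cannot be recovered. The documents do not support that. Random assignment is stated, and a list may exist. Protocol Deviations also requires prior sponsor approval in writing, or written confirmation after an emergency, so a switch treated as a deviation should leave a record. What stands is narrower: Appendix A does not capture the assignment, and no other record of it is described.

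**The enrolment sentence moves nobody between arms.** Correct. A reader might infer that it reclassifies a switched case, but use of either brand satisfies it. It matters only for a randomised case completed with neither.

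**Switching is hypothetical.** A reader might infer that failures lead to a change of brand and that this flatters the device that failed. The documents do not say why or how often a brand would be changed, nor that a failed handle would be replaced by the other brand. If the team circles the assigned stapler, the bleeding comparison is intact. The illustration also takes the unfavourable pattern, with every misplaced case bleeding and all moving the same way. These points limit the size of the concern. They do not supply the missing field or rule.

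**Conclusion.** The point holds in a limited form. The enrolment condition selects on an event after randomisation and could drop a randomised case completed with neither study stapler. Independently, Appendix A does not separate assigned from used and does not name the malfunctioning device, and no as-randomised rule settles a mixed case. Case-by-case exclusion and replacement of withdrawn subjects leave further routes by which such a case could leave the comparison.

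On assumed equal bleeding of 6/30 to 15/30 per arm, each misplaced bleeding case shifts the difference by roughly 3 to 5 points. These figures rest on assumed bleeding counts and on misplacements all in one direction. The real frequency is unknown, and if no case changes stapler there is no bias. The change is worth making because it costs little and the information is hard to rebuild afterwards. The point takes no view on when a surgeon should change stapler.

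**What to change.** 1. **Study Details:** delete the condition on use of either stapler from the enrolment sentence, so that every consented and randomised case counts.
2. **Appendix A:** replace the single circle with (a) the stapler assigned, entered before the first firing; (b) whether any firing used another stapler, which firings, and the reason; (c) if a malfunction occurred, which device.
3. **Statistics:** state that bleeding and clinical outcomes are analysed by assigned stapler with switched cases kept in, and that malfunction is attributed to the device that failed. Make the exclusion wording in Protocol Deviations and the replacement rule in Withdrawal of Subjects consistent with this.

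The cost is one deleted clause, a few lines on an existing form and a short analysis statement. The small downside is that a mixed-device case counts against its assigned stapler, which may make that device look slightly worse on bleeding.

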Endostapler Hemostasis Study Protocol

September 9, 2019

A proposed study using AEON™ Endostapler Handles and Reloads

(Lexington Medical, Inc., Billerica, Massachusetts)

Principal Investigator:

[name] (surgeon)

Co-Investigator(s):

[name] (surgeon)

[name] (surgeon)

Research Coordinator:

[name]

Primary Outcome Evaluator:

[name]

SUMMARY

The goal of this prospective, multi-center, post-market study is to measure AEON™ Endostapler performance with the EASY/THICK MODE feature for laparoscopic bariatric surgery against the Echelon Flex™ Powered Stapler system from Ethicon. Stapler performance will be evaluated primarily by incidence and degree of staple line bleeding through a third-party blinded primary outcome evaluator. The study will include 60 total consecutive cases of individuals undergoing a planned laparoscopic sleeve gastrectomy (LSG). The LSG procedure will be performed according to institutional standard-of-care and all subjects will undergo standard preoperative evaluation as well as post-operative care. Relevant data will be collected using the Data Collection sheet which should be filled out following each procedure by a member of the surgical or nursing team.

Enrollment: 60 Subjects Meeting Inclusion/Exclusion Criteria

Investigator Masking: None (Open Label)

Primary Outcome Evaluator Masking: Yes (Surgeon and Device)

Devices: AEON™ Endostapler and Echelon Flex™ Powered Stapler System

LEXINGTON MEDICAL AEON™ ENDOSTAPLER BACKGROUND

The AEON™ Endostapler is comprised of a stapler handle and reloads. The handle may accept multiple reloads of single fire cartridges. The AEON™ Endostapler devices were approved by the United States Food and Drug Administration (FDA) under the 510(k) process. Pertinent applications numbers are K171589 and K173443. Devices will be used pursuant to the indications specified in K171589 and K173443, as well as the general guidelines for use of this device on a prescription basis as outlined by the Federal Food, Drug, and Cosmetic Act (1976), and the Code of Federal Regulations Title 21 Part 800-895.

Approved Indications for Use

The AEON™ Endostapler has applications in general, abdominal, gynecologic, pediatric and thoracic surgery for resection, transection and creation of anastomoses.

Available AEON™ Endostapler Reloads

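### Outside a few listed items, adverse events enter the data only if reported as device-related, on a form that names the stapler in an open-label study

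*Combined protocol and SAP*

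**What the plan says.** The protocol's Secondary Outcome Measures contain one general safety outcome: "Incidence of reported device-related adverse events". The Appendix A sheet mirrors it with one line in the one-month block, "Reported device-related adverse events (circle", answered Yes, No or N/A, with space for details only after a Yes. No section defines device-related, sets criteria for it, or says who decides.

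The Summary gives the masking as "Investigator Masking: None (Open Label" for investigators and "Primary Outcome Evaluator Masking: Yes (Surgeon and Device" for the evaluator, whose task is to score the bleeding photographs. Under Steps and Procedures, at one week and at one month "a member of the surgical or nursing team will fill out the relevant sections of the Data Collection Sheet". The same sheet carries "Stapler Type (Circle): AEON™ Endostapler Echelon Flex™ Powered Stapler System".

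Some events have their own entries. One is "Postoperative leakage during one-month monitoring period following procedure (circle"; the others are product malfunction, dysphagia, nausea and pain at one week, and transfusion.

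Withdrawal of Subjects uses a wider notion. An adverse event of any kind may be a reason for withdrawal, and "All subjects who withdraw from the study with an ongoing adverse event must be followed until the event is resolved or deemed stable".

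**The concern.** For events outside the listed items, relatedness decides whether the event is recorded at all, when it should be an attribute of a recorded event. The dataset then holds only the product of two quantities, how often events happened and how often they were blamed on the stapler, and the two cannot be separated afterwards. In an open-label comparison of two brands, the second can differ between arms when the first does not. A gap between brands could reflect opinion, and a real difference in events that nobody attributed to the stapler would not appear in the comparison.

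The sponsor guarded against this kind of observer effect for bleeding by masking the photograph evaluator. The device-related item also depends on opinion and has no such protection. The form is also narrower than the protocol's own withdrawal rules, which treat adverse events in general as important enough to withdraw a subject for and to follow up.

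**Working it through.** The plan has no figure to reproduce: Statistics states that no formal sample size calculation was done, and no event rate is given. The check is therefore a reading of the form, followed by an illustration on assumed rates.

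**Step 1. Entries in Appendix A and whether they need attribution**

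| Entry | Attribution needed? |
|---|---|
| Product malfunction | No |
| Leakage to one month | No |
| Dysphagia, nausea (one week) | No |
| Pain, weight loss (one week) | No |
| Transfusion, during surgery and within 72 hours | Yes: staple line bleeding must be the cause |
| General adverse-event line (one month) | Yes: must be device-related |

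An event that is not in the first four rows, and is not attributed as the last two require, has no field. A readmission or reoperation judged unrelated is an example.

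**Step 2. Transfusion**

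Secondary Outcome Measures counts any transfusion during or after surgery, up to 72 hours from its start. Both form lines count only those caused by staple line bleeding. The outcome as defined cannot be computed from the form as drawn.

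**Step 3. Withdrawal**

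A subject withdrawn because of an adverse event has the usual end-of-study data collected at that point, but on the same sheet. If the event is unlisted and judged unrelated, it still has no field. The subject is then replaced, because replacement continues until 60 subjects complete. The reason for withdrawal goes into the Clinical Study Report.

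**Step 4. Illustration**

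From the protocol: 30 subjects per arm. Assumed: *r*, the share of subjects with an event outside the separately listed items, equal in both arms; and *a*, the share of those events reported as device-related, which may differ by arm.

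Recorded rate = *r* × *a*. False gap = *r* × (*a*₁ − *a*₂). Expected patients = 30 × rate.

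- Central case, *r* = 0.20, *a* = 0.50 and 0.20: 0.20 × 0.50 = 10% and 0.20 × 0.20 = 4%. The gap is 6 points. Expected patients: 30 × 0.10 = 3 and 30 × 0.04 = 1.2, a difference of 1.8.
- Low case, *r* = 0.10, *a* = 0.40 and 0.30: 0.10 × 0.10 = 1 point, or 0.3 patients.
- High case, *r* = 0.30, *a* = 0.50 and 0.20: 0.30 × 0.30 = 9 points, or 2.7 patients.

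Information is lost too. In the central case 60 × 0.20 = 12 patients are expected to have an event, and 3 + 1.2 = 4.2 would appear on this line. The other 12 − 4.2 = 7.8 would not.

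**Step 5. Would a test detect the false gap?**

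The plan names no test for this outcome, so a two-sided Fisher exact test at 0.05 is assumed. With a wider attribution contrast, 0.30 versus 0.70, the false gaps at *r* = 10%, 20% and 30% are 4, 8 and 12 points. The chance of a significant result is 0.7%, 5.7% and 13.8%. When every event is recorded it is 0.9%, 2.2% and 2.6%. A false gap would usually not reach significance. The exposure is mainly in the descriptive counts by brand.

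**The case against.** The strongest reply is that limiting a small post-market study to device-related events plus named outcomes is a legitimate design choice. The complications closest to a stapler's function, namely bleeding, leakage and malfunction, are captured separately, and bleeding is scored by a masked evaluator. That stands, and it limits the point to the general adverse-event line and, in part, the transfusion lines.

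Three stronger readings are tempting, and the documents do not support them.

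- A reader might infer that the form records nothing except device-related events. It does not: leakage, malfunction, dysphagia, nausea and pain need no relatedness judgement.
- A reader might infer that events judged unrelated are lost and the judgement can never be checked. The documents show only that the study form has no field. Standard one-week and one-month evaluations take place, the sponsor, the IRB and regulators have access to source records, and withdrawal reasons are reported. What is missing is uniform collection that allows a comparison by arm.
- A reader might take it as stated that unmasked staff judge relatedness. That is an inference from the open-label design and from who completes the sheet. It is reasonable, since no masked judge is named, but the protocol is silent.

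It is also fair to say that the illustration rests on assumed rates, that its gaps amount to fewer than three patients per arm, and that this is one of five secondary outcomes. Nothing in the documents shows that attribution will in fact differ by brand.

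**Conclusion.** The point holds in limited form. For events outside the separately listed items, entry into the data depends on a report of device-relatedness, without criteria, on a sheet that shows the stapler and is completed in an open-label study. The form is also narrower than the withdrawal section, which deals with adverse events in general.

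On assumed inputs, attribution alone could produce a gap of 1 to 9 percentage points between brands, with 6 points (1.8 patients at 30 per arm) in the central case. This rests on equal true event rates, attribution that differs by arm, and events that have no entry of their own. The size is illustrative; the missing field is a matter of record. The mismatch between the transfusion outcome and its form lines is also documentary and needs no assumption. The change should be made as a cheap improvement to a secondary safety outcome; the primary outcome is not affected.

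**What to change.** Replace the one-month line in Appendix A with: *Any adverse event from surgery to one month (Yes/No): event, date, treatment needed, judged device-related (Yes/No).* Report all adverse events by arm first. Report the device-related subset second, labelled as an unmasked judgement. The existing secondary outcome can still be derived from the last sub-item.

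Reconcile the transfusion outcome in Secondary Outcome Measures with the two transfusion lines in Appendix A, so that both count the same events.

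The cost is one reworded line on a sheet already completed at one month, with no added visits, subjects or procedures. The downside is a few more entries per arm, many of them routine postoperative events. The change removes attribution from the main comparison. It does not mask the staff who report events, so the device-related subset remains exposed, and the all-event comparison still relies on events being reported equally fully in both arms.
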